5.0 REQUIREMENTS FOR STUDY ENTRY, DURING TREATMENT, AND FOLLOW-UP

Tests and exams required before study entry are listed on [Table 1](#). Requirements following study entry are outlined on [Table 2](#).

Table 1. Tests, exams, and other requirements prior to study entry

Requirements	Prior to Study Entry	
Consent form for FC-9 signed by the patient	X	
Agreement of local Pathology department to release the primary tumor tissue ^a	X	
History & physical exam ^b	X	Within 4 weeks
Performance status (see Appendix A)	X	
Height & weight	X	
Sodium, potassium, chloride, bicarbonate or carbon dioxide, calcium, glucose, total protein, LDH	X	
Thyroid function tests: TSH ^c	X	
Urinalysis	X	
CEA	X	
PET/CT (if available) or CT scan of chest, abdomen, and pelvis with IV/oral contrast (MRI can be substituted for the CT scan) ^d	X	
APTT and INR	X	Within 2 weeks
CBC/differential/platelet count	X	
Total bilirubin (direct and indirect), AST (SGOT), ALT (SGPT), alkaline phosphatase; albumin, lipase, and amylase, creatinine, BUN	X	
Pregnancy test ^e	X	
Required study blood samples ^f	X	Prior to beginning radiation therapy
Core biopsy to procure tumor samples for submission to the NSABP Division of Pathology ^g	X	

a The archived primary tumor tissue from the diagnostic biopsy (or other previous surgery) must be requested and the Pathology department must agree before study entry to release an archived paraffin tumor block or slides if the block is unavailable (see Section 6.0). Submit the tumor tissue within 60 days after study entry. Note: With confirmation from DSSM, patients whose diagnostic sample was previously submitted for participation in NSABP MPR-1 will have met this study requirement. Provide the MPR-1 Patient ID number to DSSM for confirmation of MPR-1 tumor sample submission.
 
b Complete H&P by physician or other healthcare professional (on FDA Form 1572).
 
c If TSH abnormal, (outside normal range) obtain free triiodothyronine (T₃) and thyroxine (T₄).
 
d The same method (PET/CT scan, CT or MRI) used for baseline tumor measurements should be used at all other tumor measurement time points.
 
e For WOCBP: Pregnancy testing should be performed according to institutional standards.
 
f Blood samples collected for research study purposes should be drawn concurrently with blood samples required for study entry. See Section 6.0.
 
g This additional biopsy and overnight submission of fresh tumor samples is a study requirement. See Section 6.0. Refer to FC-9 Pathology and Correlative Science Instructions for additional information on blood and tissue collection.
		

Table 2. Tests, exams, and other requirements following study entry

Required studies (see footnote a)	Within 72 hours before Day 1 (Beginning with Cycle 1 through Cycle 4) unless indicated otherwise 1 cycle = 28 days	Within 72 hours before Day 1 (Beginning with Cycle 5 through Cycle 24) unless indicated otherwise 1 cycle = 28 days	Follow-up (Within 30 days following completion or discontinuation of study therapy)
History & physical exam ^{a,b}	X	X	X
Vital signs ^c	X	X	X
Adverse event assessment ^{b,d}	X	X	X
Measurement of target lesions ^e	X (After Cycles 2 and Cycle 4)	X (After every even cycle)	
CBC/differential/platelets	X	X	X
Sodium, potassium, chloride, bicarbonate or carbon dioxide, calcium, BUN or urea, creatinine, glucose, total protein	X	X	X
Total bilirubin, AST, ALT, alkaline phosphatase; albumin, LDH, lipase, amylase	X	X	X
CEA ^f	X (After every 2 cycles with scans)		X
TSH ^g	X (Every 2 cycles)	X (Every 2 cycles)	
Urinalysis	X	X	
Blood samples ^h	X (Day 15/Cycle 1 and Day 1/Cycles 2, 4)	X (Day 1, Cycle 6)	
Tumor sample ⁱ	X (Following completion of Cycle 2) [at 8 weeks]		

Table 2 continued on next page.

Table 2. Tests, exams, and other requirements **following study entry** (continued)

- a** At the discretion of the investigator, additional exams, bloodwork, x-rays, ECGs, scans, and other testing may be performed as clinically indicated.
- b** *Note:* Confirmation must be made that resolution of all hematologic, gastrointestinal and genitourinary toxicities are < Grade 2 before beginning the first study therapy infusion. Updated H&P with exams, adverse event assessment, and assessments during therapy and follow-up by physician or other appropriate healthcare professional (on FDA Form 1572).
- c** Vital signs (temperature, blood pressure, pulse rate, and respiratory rate) will be measured and recorded. On study therapy treatment days, vital signs will be measured within an hour prior to start of tremelimumab and durvalumab administration, at 30 minutes during the infusion (\pm 5 minutes), at the end of infusion (+ 5 minutes), and at 30 minutes (\pm 5 minutes) and 60 minutes (\pm 5 minutes) post-infusion. If the infusion takes longer than 60 minutes, then blood pressure and pulse measurements should follow the time increments as outlined at the end of the infusion or more frequently if clinically indicated. For subsequent doses of study therapy, there will be a 30 minute observation period and vital sign check between tremelimumab and durvalumab doses to monitor potential infusion-related reactions. See [Table 4](#).
- d** AE assessments 90 days (+/- 14 days) after the last dose of study therapy. Should the patient stop study therapy (e.g. due to disease progression or second primary) and begin a new treatment *prior* to the last dose of durvalumab assessment, AE assessments should be collected *only* up to the date the new therapy begins. See [Section 10.7](#).
- e** The same imaging method (PET/CT scan, CT scan or MRI), used at baseline should be used every 2 cycles from start of therapy. Assessment of measurable disease is every 2 cycles by RECIST 1.1. See [Section 11.0](#).
- f** CEA levels should be obtained every 2 cycles to correlate with disease imaging.
- g** If TSH abnormal, (outside normal range) obtain free triiodothyronine (T₃) and thyroxine (T₄).
- h** Blood samples will be collected on Cycle 1/Day 15, and prior to beginning cycles 2, 4 and 6. Blood samples collected for research study purposes should be drawn concurrently with blood samples required for study. See FC-9 Pathology and Correlative Science Instructions for required correlative study blood collection instructions. See [Section 6.0](#).
- i** Submission of core biopsy specimens of an accessible metastatic lesion collected after completion of cycle 2 (approximately 8 weeks) is a study requirement.

NOTE: Refer to the FC-9 Pathology and Correlative Science Instructions for tumor and blood sample submission instructions.

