Grade 3 diarrhea: stool frequency of ≥ 7 over baseline per day; Grade 4 diarrhea: life threatening consequences. Grade 3 colitis: severe abdominal pain, change in bowel habits, medical intervention indicated, peritoneal signs; Grade 4 colitis: life-threatening consequences, urgent intervention indicated.
 - Permanently discontinue study therapy for Grade 3 if toxicity does not improve to Grade ≤ 1 within 14 days; study therapy can be resumed after completion of steroid taper.
 - Discontinue study therapy for Grade 4.
 - Promptly initiate empiric IV methylprednisolone 2 to 4 mg/kg/day or equivalent.
 - Monitor stool frequency and volume and maintain hydration.
 - Urgent GI consult and imaging and/or colonoscopy as appropriate.
 - Report event to DSSM.
 - If still no improvement within 3-5 days of IV methylprednisolone 2 to 4mg/kg/day or equivalent, promptly start further immunosuppressives (e.g. infliximab at 5 mg/kg once every 2 weeks).
 - Caution: Ensure GI consult to rule out bowel perforation and, if administered, refer to infliximab label for general guidance before using infliximab.
 - Once improving, gradually taper steroids (28 days of taper) and consider prophylactic antibiotics, antifungals and anti PJP treatment (refer to current

NCCN guidelines for treatment of cancer-related infections [Category 2B recommendation]).

8.5.5 **Hepatitis/hepatotoxicity**
(Elevation in AST, ALT, ALP and total bilirubin)

Monitor and evaluate liver function test: AST, ALT, ALP and total bilirubin (TB). Evaluate for alternative etiologies (e.g., viral hepatitis, disease progression, concomitant medications). **Infliximab should not be used for management of immune-related hepatitis.** Prompt treatment with steroids is important per guidelines below. For study treatment dose management related to imAEs, see [Section 8.5.1](#) and [Table 7](#).

- *Grade 1 AST or ALT and/or TB elevation:*
 - Continue LFT monitoring per protocol.
- *Grade 2 AST or ALT and/or TB elevation:*

Note: For patients with metastatic liver disease who enter the study with Grade 2 transaminases, maintain dose and continue study therapy without holding. Otherwise Hold study therapy.

 - Regular and frequent checking of LFTs (e.g. every 1-2 days) until elevations are improving or resolved.
 - If no resolution to \leq Grade 1 (*or baseline*) in 1-2 days, discuss with study physician. If event is persistent ($>$ 3-5 days) or worsens, promptly start prednisone 1-2 mg/kg/day PO or IV equivalent.

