 - If still no improvement within 3-5 days despite prednisone 1-2mg/kg/day PO or IV equivalent, consider additional workup and prompt treatment with IV methylprednisolone 2-4 mg/kg/day started.
 - If still no improvement within 3-5 days despite 2-4 mg/kg/day of IV methylprednisolone, promptly start immunosuppressives (mycophenolate mofetil). Discuss with study physician if mycophenolate mofetil is not available.

Infliximab should NOT be used.

 - Once improving, gradually taper steroids (28 days of taper) and consider prophylactic antibiotics, antifungals and anti PJP treatment (refer to current NCCN guidelines for treatment of cancer-related infections [Category 2B recommendation]).
 - Report event to DSSM.

Grade 3 or 4 AST or ALT and/or TB elevation:

.For Grade 3:

- For elevations in transaminases $\leq 8 \times$ ULN, or elevations in bilirubin $\leq 5 \times$ ULN:
 - Hold study therapy dose until resolution to Grade ≤ 1 or baseline.
 - Resume study therapy if elevations downgrade to Grade ≤ 1 or baseline within 14 days and after completion of steroid taper.
 - Permanently discontinue study therapy if the elevations do not downgrade to Grade ≤ 1 or baseline within 14 days.
- For elevations in transaminases $> 8 \times$ ULN or elevations in bilirubin $> 5 \times$ ULN, discontinue study therapy.
- Permanently discontinue study therapy for any case meeting Hy's law criteria (AST and/or ALT $> 3 \times$ ULN + bilirubin $> 2 \times$ ULN without initial findings of cholestasis (i.e., elevated alkaline P04) and in the absence of any alternative cause.

Grade 4

- Discontinue study therapy.

Grade 3 or 4:

- Promptly initiate empiric IV methylprednisolone at 1 to 4 mg/kg/day or equivalent.
- If still no improvement within 3-5 days despite 1 to 4 mg/kg/day methylprednisolone IV or equivalent, promptly start treatment with immunosuppressive therapy (mycophenolate mofetil). Discuss with study physician if mycophenolate mofetil is not available.

Infliximab should NOT be used.

- Obtain a Hepatology consult, abdominal workup, and imaging as appropriate.
- Once improving, gradually taper steroids (28 days of taper) and consider prophylactic antibiotics, antifungals and anti PJP treatment (refer to current NCCN guidelines for treatment of cancer-related infections [Category 2B recommendation]).
- Report event to DSSM.

8.5.6 **Nephritis**

(serum creatinine elevation)

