8.6 Management of radiation toxicity

8.6.1 *Radiation pneumonitis*

Radiation pneumonitis is a subacute (weeks to months from treatment) inflammation of the end bronchioles and alveoli. Any patient suspected of having radiation pneumonitis should be evaluated immediately by a treating investigator. Radiation pneumonitis may present with fatigue, fever, shortness of breath, nonproductive cough, and a pulmonary infiltrate on chest x-ray.

An effort also must be made to distinguish symptoms of radiation pneumonitis from those of an immune-related event possibly related to durvalumab and tremelimumab ([Section 8.5](#) and [Table 7](#)). Pneumonitis has been observed as a toxicity associated with multiple agents blocking the PD-1/PD-L1 pathway, occurring at a frequency between 1% and 5%, and generally low grade when caught early and treated with either withholding of the agent and/or a course of steroid immunosuppression.

Given that delayed radiation toxicities may be at least in part immunologically mediated, it is possible that adding three doses of SBRT to durvalumab/tremelimumab may exacerbate the severity and/or the frequency of these events. It may therefore not be straightforward to attribute such events exclusively to durvalumab/tremelimumab or to radiation, and such events may need to be attributed to the combination.

The infiltrate on chest x-ray should include the area treated to high dose, but may extend outside of these regions. The infiltrates may be characteristically “geometric” corresponding to the radiation portal, but may also be ill defined.

Mild radiation pneumonitis may be treated with nonsteroidal anti-inflammatory agents. More significant pneumonitis will be treated with systemic steroids, bronchodilators, and pulmonary toilet. Infections should be treated with antibiotics.

8.6.2 *Radiation induced liver toxicity*

It is expected that a proportion of patients treated for right lower lobe lung or liver lesions will have transient elevation of liver enzymes following treatment. If up to Grade 3 elevation of liver enzymes is observed, more frequent measurements (at least twice weekly) of the liver enzymes are recommended until the enzymes stabilize or return to baseline levels. Repeat of blood work for all Grade 4 elevations is required at least 5 days following the first abnormal lab value to determine if the Grade 4 levels are transient (defined as lasting < 5 days) or persistent.

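### Table 2 schedules no liver panel between the pre-Cycle 1 draw and Days 26-29, right after SBRT and the first dual-checkpoint dose; adding one to the existing Cycle 1 Day 15 draw is a minor, cheap safety improvement.

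*Combined protocol and SAP*

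**What the plan says.** Protocol Section 5.0, Table 2, lists the row "Total bilirubin, AST, ALT, alkaline phosphatase; albumin, LDH, lipase, amylase" under the column headed "Within 72 hours before Day 1 (Beginning with Cycle 1 through Cycle 4", with matching entries for later cycles and follow-up. The row has no mid-cycle entry.

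SBRT is given on Days -2, -1 and 0 (Section 14.1) to a single lung or liver lesion (Appendix B, 1.3). Both drugs follow on Day 1 of a 28-day cycle (Section 7.1, Table 4). Section 8.6.2 expects that "a proportion of patients treated for right lower lobe lung or liver lesions will have transient elevation of liver enzymes following treatment".

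The rules for closer testing depend on a finding:

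- Section 8.6.2: "If up to Grade 3 elevation of liver enzymes is observed, more frequent measurements (at least twice weekly" or more often, recommended until enzymes stabilize or return to baseline.
- Section 8.5.5, Grade 2: "Regular and frequent checking of LFTs (e.g. every 1-2 days) until elevations are improving or resolved". For Grade 1, monitoring simply stays on the protocol schedule.

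Treatment also depends on a finding. For a Grade 2 elevation that worsens or persists beyond 3-5 days, 8.5.5 says to "promptly start prednisone 1-2 mg/kg/day PO or IV equivalent"; for Grade 3 or 4 it says "Promptly initiate empiric IV methylprednisolone at 1 to 4 mg/kg/day or equivalent".

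A mid-cycle venipuncture already exists. Table 2 footnote h states: "Blood samples will be collected on Cycle 1/Day 15, and prior to beginning cycles 2, 4 and 6". These are research samples. The footnote wants them taken together with clinical bloods, but Table 2 lists no clinical blood test for Day 15.

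**The concern.** The protocol predicts liver enzyme elevation after SBRT in some patients and starts two checkpoint inhibitors the day after the last fraction. It then schedules no liver test for about four weeks. The panel before Cycle 1 cannot show the effect of either treatment, because it is drawn before the first infusion and while SBRT is under way or barely over.

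Table 2 footnote a allows extra bloodwork when clinically indicated, but an elevation without symptoms gives no indication. The weekly calls and monthly reviews in Section 14.3 order no test. What is at stake is the time until a silent, continuing elevation is found and handled under 8.5.5. Both the close monitoring and the steroid steps there assume that someone has already measured it.

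**Working it through.** The documents state no figure for this interval, so it is built from the schedule.

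**Inputs.** SBRT on Days -2, -1, 0 (14.1). Cycle of 28 days, so Cycle 2 Day 1 is Day 29. Panel within 72 hours before Day 1 (Table 2): Days -2 to 1 for Cycle 1 and Days 26 to 29 for Cycle 2. Dosing may move 3 days either way (8.2), which widens the second range to Days 23 to 32. Research draw on Day 15 (footnote h).

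**Interval without a scheduled panel**

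| Interval | On schedule | With 3-day window |
|---|---|---|
| Last fraction (Day 0) to next panel | 26 - 0 = 26 to 29 - 0 = 29 days | 23 to 32 days |
| Panel to panel | 26 - 1 = 25 to 29 - (-2) = 31 days | 23 - 1 = 22 to 32 - (-2) = 34 days |
| Pre-Cycle 1 panel to Day 15 | 15 - 1 = 14 to 15 - (-2) = 17 days | same |
| Day 15 to pre-Cycle 2 panel | 26 - 15 = 11 to 29 - 15 = 14 days | 23 - 15 = 8 to 32 - 15 = 17 days |

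**Delay in finding an elevation that persists.** Delay = first scheduled draw on or after onset day s, minus s. The documents do not say when an elevation begins, so two patterns are assumed.

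- *Onset uniform over Days 2-29, second panel on Day 29.* Now: 29 - s runs from 0 to 27, mean 13.5 days. With Day 15: onsets on Days 2-15 and on Days 16-29 each give delays of 0 to 13, mean 6.5 days.
- *Onset uniform over Days 1-10 (mean 5.5).* Now: 26 - 5.5 = 20.5 days to 29 - 5.5 = 23.5 days. With Day 15: 15 - 5.5 = 9.5 days.

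**Share of self-resolving elevations seen by a scheduled draw.** An elevation lasting d days is seen if a draw falls between s and s + d - 1. Under uniform onset the share is d/28 now and 2d/28 with Day 15 (for d up to 14). For onset on Days 1-10, onsets are counted out of 10, with the second panel on Days 26-29.

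| Duration | Uniform: now | Uniform: with Day 15 | Days 1-10: now | Days 1-10: with Day 15 |
|---|---|---|---|---|
| 4 days | 14% | 29% | 0% | 0% |
| 7 days | 25% | 50% | 0% | 20% |
| 10 days | 36% | 71% | 0% | 50% |
| 14 days | 50% | 100% | 0% | 90% |

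The documents give one relevant duration: 8.6.2 calls a Grade 4 elevation transient if it lasts under 5 days. The 4-day row therefore deserves the most weight, and it shows little gain. The larger gains rest on durations chosen for illustration.

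**Radiation-induced liver disease.** Section 8.6.2 places onset 2 weeks to 3 months after liver radiation, roughly Day 14 to Day 90 from the last fraction. The panels before Cycles 2, 3 and 4 fall on Days 26-29, 54-57 and 82-85, all inside that window. Day 15 falls at its start.

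**Steroid timing after a Day 15 finding.** A 28-day taper begun on Day 15 ends on Day 15 + 28 = 43. In practice it would end later, since Grade 2 steroids wait for persistence beyond 3-5 days and tapering waits for improvement. Cycle 2 is due on Day 29. Under 8.2.1, therapy resumes on Day 1 of the next scheduled cycle, nominally 29 + 28 = Day 57.

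**The case against.** The strongest case against the change is that it searches for something the protocol regards as benign. The elevation foreseen in 8.6.2 is transient, and the response there is repeat measurement, without steroids. Steroids come from 8.5.5, which concerns immune-mediated hepatitis and asks for other causes to be evaluated. Both drugs are given only on Day 1, always after a panel within 72 hours. Site contact at the Day 15 draw, the weekly calls, and the SBRT volume and liver dose limits in Appendix B lower the remaining risk. Finding self-limiting elevations could lead to steroids during an immunotherapy efficacy test and cost evaluable patients in a study of 12 to 21.

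Much of this stands and sets the size of the point. It does not close the gap, because none of these safeguards measures liver enzymes between the two panels. The burdens of detection come from the protocol's own management rules, so they are a cost to weigh and not a reason to leave the interval untested.

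Three stronger readings are tempting, and the documents support none of them:

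- *Patients are dosed without current liver results.* They are not; a panel precedes every dose.
- *Radiation-induced liver disease would be missed.* The later pre-cycle panels already sample its window.
- *A Day 15 panel would catch the expected transient elevations.* If they last under 5 days, it mostly would not.

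**Conclusion.** The concern holds as a minor safety improvement. No liver panel is scheduled for 26-29 days after the last fraction, or 25-31 days from panel to panel, and that follows directly from Table 2. The two figures should be kept apart: a reader might take 25-31 days as time since SBRT, but that range runs from the pre-Cycle 1 panel.

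The benefit is earlier detection of a silent elevation that persists. The mean delay falls by about half or somewhat more under both assumed onset patterns. The size rests on those patterns and on draws near schedule.

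The documents give no rate of liver enzyme elevation after this treatment, so the number of patients who would benefit cannot be computed. A reader might infer that steroid treatment is being delayed in many patients; nothing in the documents shows that the expected elevations persist or need steroids.

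**What to change.** In Table 2, add total bilirubin, AST, ALT and alkaline phosphatase to the Cycle 1 Day 15 draw, at minimum for patients whose SBRT target is in the liver or right lower lobe.

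Direct cost: one table entry and one local panel per patient at an existing venipuncture, with no new visit. That means 12 to 21 evaluable patients plus any who are replaced, and fewer if limited by target site, a split the documents do not give. The change helps only patients who have not yet passed Cycle 1 Day 15.

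Indirect cost: transaminase increases are adverse events of special interest (10.2), so each one found at Grade 2 or above needs an expedited report within 24 hours (10.4.2, 10.7.2), plus repeat tests and possibly a hold or steroids. If steroids start, the taper ends no earlier than about Day 43. The Cycle 2 dose would then be held, possibly to the next scheduled cycle, and a taper longer than 28 days ends study therapy (8.2.1). A patient who therefore does not complete Cycles 1 and 2 is non-evaluable and is replaced (14.2).

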6.0 PATHOLOGY AND CORRELATIVE SCIENCE STUDIES

6.1 Overview of requirements

Collection and submission of all patient samples (blood, tumor) as listed below is a requirement for all patients participating in the NSABP FC-9 study. ***By signing the FC-9 consent form, the patient has agreed to all required sample collections and submissions.***

Non-submission of required patient samples will be a protocol violation.

Table 3. Summary of FC-9 patient sample submission requirements

Study Requirements for ALL Patients (unless indicated otherwise)	Prior to Study Entry	Before radiation therapy begins (Prior to Day -2)	Cycle 1, Day 15	Up to 3 days prior to Day 1 of Cycles 2, 4 and 6 Therapy Begins
Submission of treatment-naive tumor (primary or metastatic diagnostic tumor [FFPE block])	Yes ^a	N/A		N/A
Submission of fresh tumor samples ^b	Yes			Yes (Following completion of cycle 2 [at 8 weeks])
Collection & submission of blood samples ^c	Yes		Yes	Yes

a Archived paraffin block of primary tumor tissue is preferable. Refer to FC-9 Pathology and Correlative Science Instructions for acceptable alternative submissions.
Note: After confirmation by DSSM, patients whose diagnostic sample was previously submitted for participation in NSABP MPR-1 will have met this study requirement. Provide the MPR-1 Patient ID number to DSSM for confirmation of MPR-1 tumor sample submission.

b Submission of core biopsy specimens of an accessible metastatic lesion collected prior to beginning radiation therapy and following completion of Cycle 2 (at 8 weeks on study therapy) is a study requirement.

c Blood sample collections: Pre-treatment *prior* to beginning radiation therapy, Day 15 of Cycle 1, and Day 1 of Cycles 2, 4, and 6. See [Section 6.3.2](#).

Refer to the FC-9 Pathology and Correlative Science Instructions for tumor and blood sample submission instructions.

